4.3 RANDOMISATION

Participants will be allocated into one of four trial arms following baseline assessments, using stratified randomisation (Suresh, 2011), based on gender, BMI, and free sugar intakes (%TEI) at baseline, as variables that may affect our outcomes. Randomisation will be undertaken by a researcher with no direct contact with participants using a random number generator, before the trial start. Group allocations will be concealed using opaque envelopes.

5 INTERVENTION / CONTROL

There will be four trial arms: three arms delivering different types of recommendations for reducing free sugars and one control arm. All dietary recommendations have been gained from current publicly available information (NHS, 2018, 2019; Diabetes UK, 2021).

5.1.1 Group N: Nutrient-based guidelines

The nutrient-based recommendations begin with the instruction: '*Your dietary recommendation is to reduce your intake of free sugars to less than 5% of your total energy intake*'. This sentence will be followed by one page of nutrient-based information, including the different names for sugars and how to identify the sugar content of foods, e.g. '*high in sugar – 22.5g or more of total sugar per 100g*'. Current recommendations from PHE (NHS 2018) have been amended to provide only the nutrient-based information that relates to sugars.

5.1.2 Group NF: Nutrient- and Food-based guidelines

These recommendations begin with the instruction: '*Your dietary recommendation is to reduce your intake of free sugars to less than 5% of your total energy intake. To aid with this, reduce your intake of foods high in free sugar*'. Participants will then be provided with the same nutrient-based information as Group N plus four additional pages detailing which foods are commonly high in free sugars and examples of how much sugar is included, e.g. '*A bowl of sugary breakfast cereal could contribute 70g of sugar (up to 22 sugar cubes) to your diet over a week*'. Current recommendations from PHE (NHS 2018, 2019) have been amended to provide the nutrient- and food-based information that relates to sugars.

5.1.3 Group NFS: Nutrient-, Food- and Food-Substitution-based guidelines.

These recommendations begin with the instruction: '*Your dietary recommendation is to reduce your intake of free sugars to less than 5% of your total energy intake. To aid with this, reduce your intake of foods high in free sugar and replace these with low sugar versions*'. Participants will be provided with the same nutrient- and food-based information as Group NF, plus five additional pages on low-calorie sweeteners (LCS) and low sugar versions of foods. This information details what LCS are, where they are found, their different uses, and suggests low sugar substitutions for high sugar products, e.g. '*biscuits – swap for oatcakes, oat biscuits, or unsalted rice cakes*'. This information has been gained from Diabetes UK (Diabetes UK, 2021) and includes only details on LCS with removal of all references to diabetes.

5.1.4 Control Group

The control group are given no dietary recommendations.

5.1.5 Intervention Delivery

Interventions will be delivered to participants in a sealed envelope, alongside a user guide for *Nutritics Libro App* (Nutritics, 2019), and an instruction '*to keep an accurate diet diary using the Nutritics software*'. This instruction has been carefully worded, such that for participants in the control group, this instruction can be construed as a dietary recommendation. All groups will receive the same instructions regarding the diet diaries, but this construal is intended to aid blinding and compliance for those in the control group. Envelopes will be packaged to include the same number of pages regardless of intervention (through the addition of blank pages) to maintain researcher blinding. Full copies of each intervention, as provided to participants, are included in the Supplementary Materials.

Participants will be provided with their recommendations following baseline measures. Participants will not be permitted to ask questions on the recommendations, as is currently the scenario for the UK public where dietary recommendations are provided, e.g. via government slogans and TV adverts, without the opportunity to ask questions. An inability to ask questions will also ensure that the same information is provided to all participants, maintaining intervention fidelity. Activities undertaken to adhere to the recommendations, e.g. information gathering, LCS use, will be assessed among the outcomes of the study.

5.2 BLINDING

All envelopes containing the intervention information will be identical, sealed and coded by the researcher undertaking the randomisation. The researcher in direct contact with participants will be kept blinded to treatment allocation throughout data collection. It is impossible to blind participants, however, participants will be blinded to the true purpose of the trial and to other interventions used. To further disguise the purpose of the trial, all participants will complete several questionnaires in addition to those focusing on sugar.

6 TRIAL OUTCOMES

Our primary outcomes are % changes in free sugar intakes and adherence to the dietary recommendations over a 12 week period. Secondary outcomes are: daily energy intake, dietary composition, anthropometry, sweet food perceptions and preferences, sweet food choice, attitudes to sweet foods, attitudes towards eating behaviour, motives for food choice, knowledge and lifestyle variables, quality of life and adverse events. Secondary qualitative outcomes are: barriers and facilitators towards intervention adherence and success/failure in achieving the recommendations. Sweet liker status, PROP status, and demographic variables will also be assessed to aid in the interpretation of all outcomes.

6.1 FREE SUGAR INTAKES

Change in free sugar intakes, as %TEI, will be assessed using diet diaries, undertaken using the *Nutritics software platform* and 'Libro' App (Nutritics, 2019). Usual dietary intakes will be calculated from three days of diet diaries (1 weekend day and 2 weekdays) (National Cancer Institute) at baseline and 12 weeks.

Alongside changes in free sugar intakes, participants will also be recorded as 'successful' in achieving the dietary recommendation, where free sugar intake is $\leq 5\%$ TEI, or 'not successful' where free sugar intake remains $> 5\%$ TEI.

6.2 ADHERENCE

Adherence to the dietary recommendations will also be assessed by diet diaries. Eighteen daily diet diaries, in addition to the three diaries at baseline and at 12 weeks, will be undertaken over the 12-week intervention, as identified in **Table 1**.

Table 1:

Scheduled diet diary recording to measure compliance.

	Monday	Tuesday	Wednesday	Thursday	Friday	Saturday	Sunday
Baseline	DD	*	DD	*	*	DD	*
Intervention provided							
Week 1	DD			DD			DD
Week 2			DD			DD	
Week 3		DD			DD		
Week 4	DD			DD			DD
Week 5				DD			
Week 6			DD				
Week 7		DD					
Week 8	DD						DD
Week 9						DD	
Week 10					DD		
Week 11				DD			
Week 12	DD		DD			DD	

DD = Diet diary, including perceived adherence questions

Adherence will be classified five times across the 12-week intervention. During the first two weeks of the trial, adherence will be based on participant ability to reduce free sugars by $\geq 2\%$ TEI from baseline or not, classified as 'adherent' or 'non-adherent' respectively. Participants will then be classified at weeks 4, 8 and 12 using data on their ability to reduce

free sugars by $\geq 2\%$ TEI from previous assessment (baseline for week 4), and their answers to the following adherence question: 'Are you currently following the dietary recommendations you were given?' Reductions of free sugar intakes $\geq 2\%$ TEI and an answer 'YES' will result in a classification of 'active adherent', reductions of free sugar intakes $\geq 2\%$ TEI and an answer 'NO' will result in a classification of 'passive adherent', reductions of free sugar intakes $< 2\%$ TEI and an answer 'NO' will result in a classification of 'active non-adherent', and reductions of free sugar intakes $< 2\%$ TEI and an answer 'YES' will result in a classification of 'passive non-adherent'.

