8.3 ANALYSES THREE: BARRIERS AND FACILITATORS TOWARD DIETARY CHANGE

Qualitative data will be transcribed and analysed using thematic analysis following Braun and Clarkes 6-stage methodology (Braun and Clarke, 2006). These analyses will be aided by the use of NVIVO software, and reported using the Consolidated Criteria for Reporting Qualitative Research (COREQ) (Tong et al., 2007). Themes will be gained from the population as a whole, at different time points, and interpreted in combination with the data on free sugar intakes and adherence. Comparisons will be made between those who are successful and not successful at changing their free sugar intakes, and those who are adherent and not adherent to the recommendations.

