Where SPSS did not automatically pool results, Rubin's Rules for combining single estimates were used. The same multiple imputation guidelines were used for the basis for the imputation of all missing data. Where variables presented as having missing data, they were set as 'impute only' to ensure all predictor variables were not based on imputed data. The only difference was in one baseline waist circumference value that was missing in the original data and used in the 2nd MI predictors of the subsequent variables. This study took the premise of not generating imputations based on imputed data values. The same multiple imputation model was run for the initial analyses, adherence and variables completed by only lab participants. Multiple imputation for the adherence data used the same methods and predictors as for the main data set. The step by step methods used are included below. Adherence data points of each free sugar intake at each dietary data point were not included as predictors due to the fact that at least 1 time point needed to be imputed at each variable time point.

Instructions for multiple imputation in SPSS

1. Go to transform – random number generator. Select and set the active generator initialization at a fixed value of 950.
 - a. (This step is to provide a starting point/seed for the MI to enable results to be reproduced)
2. Then Analyze – multiple imputation – impute missing data values.
 - a. Variables tab
 - i. Input all variables for the model in the order they are to be used (this can be found in the output document and also to summarise at the end of this doc) but is all endpoint and corresponding baseline variables, therefore excluding demographics. But including gender. (The order is central for reproducing)
 - ii. Create a new data set – name ComA1_Impu
 - iii. Change imputations to 20
 - b. Method tab
 - i. Custom – select fully conditional specification (set to 50 iterations)
 - ii. Model type – change to PMM – chose from 5 closest (as is default)
 - c. Constraints tab
 - i. Scan data
 - ii. Under define constraints – set all Endpoint variables as impute only.
 1. Instead of clicking use tab and I, plus directional keys to change this.
 - d. Output tab
 - i. Tick imputation model, descriptive statistics and create iteration history – name ComA1_iter
 - e. Double check – click ok
3. Save the imputed and iterations files.

Sequence for multiple imputation.

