BLNFS, BLDGendermale1female2, BLBMI, BLNEnergykcal, BLNCarbohydrateg, BLNProteing, BLNFatg, BLN Sugarsg, BLNFreeSugarsg, BLNFibreg, BLNSaturatedFatg, BLSSodiumNamg, BLWeightkg, BLWaistcircumferencecm, BLLTEShealthscore, BLFCQ1Health, BLFCQ2Mood, BLFCQ3Convenience, BLFCQ4SensoryAppeal, BLFCQ5NaturalContent, BLFC1Q6Price, BLFCQ7WeightControl, BLFCQ8Familiarity, BLFCQ19EthicalConcern, BLSQPC1Personalimpact, BLSQPC2Personalmanagement, BLSQPC3Nonchalance, BLSQPC4Negativity, BLSQPC5Perceivedunderstanding, BLSQPC6PerceivedNonautonomy, BLSF36PCS, BLSF36MCS, BLTSEQ CR, BLTSEQQUE, BLTSEQEE. *Followed by imputation only variables

Get pooled descriptives for analysis / comparison to my values.

1. Data - Split file
 - a. Click split file in ComA1_imp
 - b. Click compare groups
 - c. By imputation number_variable
 - d. Ok
2. Analyze – Descriptive statistics
 - a. Descriptives
 - b. Input all BL and EP variables apart from BL OG FS%.
 - c. Scroll to bottom of output table for pooled means – SD will be calculated from average of 20 imputations at a later date and are not shown here.

BLINDING

The main researcher had no knowledge of allocated groups of participants and was blinded during all data handling and imputation.

DATA ANALYSIS

Outcomes

Primary outcomes were % TEI from free sugars (%FS), and adherence to the recommendations at 12 weeks. Secondary outcomes were dietary profiles (daily energy intake, dietary composition, food consumption), anthropometry, sweet food perceptions and preferences, sweet food choice, attitudes to sweet foods, attitudes towards eating behaviour, motives for food choice, knowledge and lifestyle variables, quality of life and adverse events at week 12; change between baseline and week 12 in key outcomes (%FS, daily energy intake, sugar-sweetened and sweetener-sweetened food consumption, anthropometry), %FS, adherence, dietary profiles and barriers and facilitators towards intervention adherence and success/failure in achieving the recommendations (subset only) at weeks 1, 2, 4 and 8. Demographic variables, and sweet taste sensitivity, sweet liker status and PROP (bitter taste) status were also assessed at baseline, to aid in the interpretation of all outcomes, considering associations between these variables and sweet taste perceptions, liking and food intakes (Jayasinghe et al., 2017; Yeomans et al., 2009).

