Three distinct analyses were pre-specified in advance: 1) Analyses of the population as a whole to investigate the effects of the three different types of dietary recommendation versus control; 2) Analyses of the effects of the dietary recommendations in different population subgroups, and 3) Investigation of the barriers and facilitators to success.

Data presentation

Data will be presented as mean \pm standard deviation in all cases, unless stated. Values will be considered significant at the $p<0.05$ level. Before completing analyses, data will be checked for normality. The data set is large, $N=242$, thus a normal distribution will be assumed. Where assumptions of homogeneity of variance are violated (Levene's test $p<0.05$), statistics will be taken from analyses conducted assuming non-equal variances. Bonferroni corrections for multiple testing will be applied to data where tests were not pre-specified in the study protocol. Where multiple regression analyses are used, all variables will be checked for multicollinearity using correlation cut-offs of <0.7 . Pearson correlation values will be used for all continuous variables, and Spearman correlations for categorical variables.

Participant characteristics

Details of study completion will be provided and a CONSORT diagram created detailing number randomized to each group, number completing the study in each group, drop out and number included in all analyses.

Characteristics will be given for the whole sample and for each trial group.

Analyses One: Quantitative Data

For analyses one, multiple regression analyses will be used. Analyses will be conducted for both primary outcomes, for key secondary outcomes - daily energy intake, sugar-sweetened food intake, LCS-sweetened food intake, body weight, waist circumference, and adverse events; and change (baseline - week 12) data for these outcomes; and for other secondary outcomes (dietary

composition, sweet food perceptions and preferences, sweet food choice, attitudes to sweet foods, attitudes towards eating behaviour, motives for food choice, knowledge and lifestyle variables, quality of life) if differences are found in the sample as a whole from baseline to week 12. This will reduce the number of exploratory tests undertaken. Differences from baseline to week 12 will be investigated by paired t-tests. Primary outcomes and outcomes associated with dietary composition will also be investigated in the same manner at weeks 1, 2, 4 and 8.

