Primary models will include gender, age, control/intervention group, baseline %FS, baseline body weight (as randomization variables), and baseline variable of interest. In analyses for %FS, sugar-sweetened food intake, LCS-sweetened food intake, body weight and waist circumference, TEI at Week 12 and physical activity at Week 12 will also be included. Secondary models will also include any additional variable that correlates with each outcome when assessed independently. All variables measured will be considered as secondary variables. Effects for all continuous variables will be investigated using linear multiple regression. Effects for adherence will be investigated using logistic regression to predict adherent vs not adherent.

Analyses Two: Quantitative Data

For analyses two, analyses one will be repeated for demographic groups where significant associations for these variables were found in analyses one. Analyses will only be conducted if significant associations are reported. If no significant associations with demographic variables are found, these analyses will not be completed. These analyses are intended to demonstrate differing effects of the intervention/s in different population groups.

Analyses Three: Qualitative Data

Analyses three will investigate the qualitative data collected from a subset of participants using solo interviews. These interviews were scheduled for completion in a sample of 80 participants from different intervention groups and at different time points. These analyses will be undertaken using a thematic framework analysis. First, a random sample of interviews will be analysed inductively using thematic analysis to identify codes. These codes will be used to create a framework and the framework then applied to all interviews.

Framework analysis has been chosen as a suitable analytical method for evaluating the qualitative interview data gathered, due to an interest in individual experiences and seeks to identify the different factors (barriers or facilitators) that contributed to successful or unsuccessful dietary change (Braun & Clark, 2013). The practical methods for conducting framework analysis follow a methodology as outlined below.

Framework analysis (Braun & Clarke, 2006; 2013; Gale et al, 2013).

Phase 1 'Familiarizing yourself: Transcribing data (if necessary), reading and re-reading the data, noting down with your data: initial ideas'.

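### The week 8 and week 12 adherence labels need a fresh drop of at least 2% TEI since the previous assessment, so a reduction made by week 8 and then held counts as non-adherent on a co-primary outcome.

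*Protocol*

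**What the plan says.** Protocol section 6.2 sets five adherence classifications, all with a threshold of 2% TEI.

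- **Weeks 1 and 2:** the reduction is measured as "TEI from baseline or not, classified as 'adherent' or 'non-adherent' respectively".
- **Weeks 4, 8 and 12:** the reduction is measured as "TEI from previous assessment (baseline for week 4), and their answers to the following adherence question". It is combined with a yes/no question on whether the participant is following the recommendations, giving four labels. A reduction below the threshold with the answer YES "will result in a classification of 'passive non-adherent".

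The SAP (Data Analysis, Outcomes) states: "Primary outcomes were % TEI from free sugars (%FS), and adherence to the recommendations at 12 weeks". Under Analyses One it adds "Effects for adherence will be investigated using logistic regression to predict adherent vs not adherent" and, for the earlier time points, "Primary outcomes and outcomes associated with dietary composition will also be investigated in the same manner at weeks 1, 2, 4 and 8". The available SAP text does not restate how adherence is derived. Protocol section 8.3 also compares "those who are adherent and not adherent to the recommendations" in the qualitative work.

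**The concern.** The parenthesis in section 6.2 exempts week 4 only. Read as written, a participant must lose a further 2 points between weeks 4 and 8 to be adherent at week 8, and another 2 points between weeks 8 and 12 to be adherent at week 12. The recommendations in Protocol sections 5.1.1 to 5.1.3 ask participants to get below a level, 5% of energy. They do not ask for a continuing fall. Someone who follows the advice promptly and keeps to it is recorded as a failure at the visit that defines the primary outcome, and answering YES does not change that.

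The week-12 logistic regression compares arms on this label. If the intervention effect is in place by week 8 and held, the label carries no information about it. A null or reversed adherence result could then be reported as failure of the recommendations.

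**Working it through.** The plan gives no expected adherence rate or power for adherence, so there is no figure of its own to reproduce.

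**Step 1: apply the rule to example intakes.** No statistical assumption is needed. Values are %TEI at baseline, week 4, week 8 and week 12; labels are for weeks 4/8/12 (Y = reduction criterion met).

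| Intakes | As written | From baseline |
|---|---|---|
| 12, 8, 8, 8 | Y/N/N | Y/Y/Y |
| 12, 12, 8, 8 | N/Y/N | N/Y/Y |
| 12, 9, 7, 5.5 | Y/Y/N | Y/Y/Y |
| 7, 4, 4, 4 | Y/N/N | Y/Y/Y |
| 12, 12, 15, 13 | N/N/Y | N/N/N |

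The fourth participant is successful under Protocol section 6.1 (≤5% TEI) yet non-adherent at weeks 8 and 12. The fifth is adherent at week 12 while above baseline. Being adherent at all of weeks 4, 8 and 12 needs a total fall of 3 × 2 = 6 points. That is impossible from a baseline below 6% TEI, although entry requires only more than 5%. Anyone below 2% TEI at week 8 cannot be adherent at week 12.

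**Step 2: proportion labelled adherent.** Inputs:
- 48 evaluable per arm: 60 × (1 − 0.20), from Protocol section 4.2.
- Two-sided 5% test. Section 4.2 gives alpha 0.05; two-sided is assumed.
- SD of the error in each diary mean: 2.5 points, range 1.5 to 3.5. This is an assumption. Section 4.2's 2 points / 0.8 also gives 2.5.
- No true change in control, independent errors of equal size, and both adherent labels (active and passive) counted as adherent. All are assumptions.

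With D the true fall between the two assessments compared,

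P(adherent) = 1 − Φ((2 − D) / (√2 × SD)).

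At SD 2.5, √2 × SD = 3.536:
- D = −1: 1 − Φ(0.849) = 0.198
- D = 0: 1 − Φ(0.566) = 0.286
- D = 1: 1 − Φ(0.283) = 0.389
- D = 1.5: 1 − Φ(0.141) = 0.444
- D = 2: 1 − Φ(0) = 0.500
- D = 3: 1 − Φ(−0.283) = 0.611

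**Step 3: power for two proportions.** Power ≈ Φ((d − 1.96·se₀)/se₁), plus the negligible opposite tail, where se₀ uses the pooled proportion and se₁ the separate ones. For 0.611 against 0.286: d = 0.325, se₀ = 0.1015, se₁ = 0.0960, so Φ(1.31) = 0.91.

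| True course in the intervention arm | Rule as written: control vs intervention | Power | From baseline: control vs intervention | Power |
|---|---|---|---|---|
| Week 12: 3-point drop by week 8, held | 28.6% vs 28.6% | 5% | 28.6% vs 61.1% | 91% |
| Week 12: 2 points by week 8, 3 by week 12 | 28.6% vs 38.9% | 19% | 28.6% vs 61.1% | 91% |
| Week 12: 1 point by week 8, 3 by week 12 | 28.6% vs 50.0% | 58% | 28.6% vs 61.1% | 91% |
| Week 12: 4 points at week 8, rebounding to 3 | 28.6% vs 19.8% | wrong direction | 28.6% vs 61.1% | 91% |
| Week 8: 1.5 points by week 4, 3 by week 8 | 28.6% vs 44.4% | 36% | 28.6% vs 61.1% | 91% |

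Over SD 1.5 to 3.5, the 91% becomes 65–100%, the 19% becomes 12–38% and the 58% becomes 34–94%. The 5% does not move: when D = 0 in both arms the two proportions are equal at any SD.

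**The case against.** The literal reading of section 6.2 is not in dispute. The main objections are these.

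- **Pooling is assumed.** The SAP does not say that active and passive adherent are combined. If only active adherent counted, arms could differ through the YES answers alone. With 28.6% meeting the drop in each arm and assumed YES rates of 80% vs 60%, power is about 11%; with 90% vs 50%, about 29%. The 5% figure is therefore conditional on pooling. Pooling is nevertheless the natural reading of the labels, and a contrast made only by self-report does not repair the drop criterion.
- **The 91% is favourable.** Controls keep the same diaries, and Protocol section 5.1.5 words that instruction so that it can pass for a recommendation. If control fell by 1 point, power from baseline would be 59% at SD 2.5 and 35% at SD 3.5. That stands, but it lowers only the comparator. Table 1 also schedules three, two and three diaries in weeks 4, 8 and 12, so equal noise is a simplification.
- **Relapse and recovery.** Someone who relapses by week 8 and recovers to at least 2 points below baseline is adherent under either rule. The true reverse error needs a case such as 12, 12, 15, 13.
- **Redundancy.** A pooled, baseline-referenced label is close to a dichotomised version of the other primary outcome. This is a real limit on what the repaired outcome adds.
- **Scope.** Section 8.3 does not say which classification it uses, so the effect on the qualitative comparison is possible rather than certain. The sample size rests on free sugar intake, which is unaffected.

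**Conclusion.** The concern holds: the definition is wrong as written for weeks 8 and 12, and week 12 is a primary outcome, so it must be fixed. That a held reduction is labelled non-adherent follows from the text alone. The size rests on assumptions. With pooled labels, equal noise across arms and no change in control, an effect held from week 8 leaves 5% power whatever the SD. For a 3-point drop, the same data referenced to baseline give 91% (65–100% over SD 1.5 to 3.5). Some power remains if intake keeps falling after week 8, and the contrast reverses if it partly rebounds.

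The defect is confined to the week 8 and week 12 adherence labels and analyses that use them. It is also assumed that the protocol rule carries into the SAP. The Supplementary Materials and part of the SAP were not available, so a redefinition there cannot be excluded.

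**What to change.** Define adherence at weeks 8 and 12 as a reduction of at least 2% TEI from baseline, as already done for weeks 1, 2 and 4. Keep change since the previous assessment as a descriptive measure of maintenance or relapse. State in the SAP that active and passive adherent together form the adherent category in the logistic regression, and which diaries supply the week 4 and week 8 values. Keep success at ≤5% TEI as a separate measure.

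No new data are needed. The SAP's imputation section says "Adherence data points of each free sugar intake at each dietary data point were not included as predictors", in an account of imputing intake at those time points, so the label can be recomputed within each imputed set. The cost is a dated amendment to protocol and SAP and a re-derived variable. The SAP describes diary processing and imputation as done, so this changes a primary outcome after data collection and needs a recorded reason. The SAP's Blinding section says the main researcher was blinded through data handling and imputation, so a blinded re-derivation may still be possible. If allocation has been revealed, report both definitions and say which was planned.
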